5.5.3 Antibiotic spectrum and antibiotic intensity score

The antibiotic intensity score will be determined as follows: Each antibiotic is assigned an antibiotic spectrum rank from 1-5 (see Table 4). The antibiotic rank will be multiplied by the duration each antibiotic is received (in hours) within the first 72 hours following randomization. For patients receiving multiple antibiotics, the total antibiotic intensity

score will be the summation of the rank x duration product for each antibiotic. If a single dose of antibiotic is administered, duration will be considered 1 hour. For all antibiotics given for more than one dose, the duration will be the time of administration of the last dose minus the time of administration of the first dose (or time of randomization, if subject was receiving antibiotic at randomization) plus one hour. Patients who die before 72 hours will be assigned the highest intensity score among patients in the study who were alive at 72 hours.

Table 4. Antibiotic spectrum rank, categorized by clinical use and spectrum

Intensity score	Rank	Antibiotics
1	Narrowest	Amoxicillin, ampicillin, first-generation cephalosporins, clindamycin, dalbavancin, daptomycin, dicloxacillin, linezolid, macrolides, metronidazole, nafcillin, oritavancin, oxacillin, penicillin, quinupristin/dalfopristin, rifampin, tedizolid, vancomycin
2	Medium narrow	Amoxicillin/clavulanic acid, ampicillin/sulbactam, 2 nd -generation cephalosporins, 3 rd generation cephalosporins (except ceftazidime), PO fluoroquinolones (ciprofloxacin, moxifloxacin, levofloxacin), tetracyclines, trimethoprim-sulfamethoxazole,
3	Medium	Aminoglycosides (amikacin, gentamicin, tobramycin), ceftaroline, ceftazidime, IV fluoroquinolones (ciprofloxacin, moxifloxacin, levofloxacin), fosfomycin
4	Medium broad	Anti-Pseudomonal penicillin/penicillinase combinations, aztreonam, cefepime, ertapenem
5	Broadest	Anti-Pseudomonal carbapenems, ceftazidime/avibactam, ceftolozane/tazobactam, polymyxins, tigecycline

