7.2.3 Exploratory Analyses

- Standardized costs, obtained from the UHC/Vizient database
- The primary endpoint will be analyzed comparing patients who are:
 - in the ICU at baseline versus not in the ICU at baseline
 - neutropenic at baseline versus not neutropenic at baseline
- The primary endpoint will be analyzed excluding antibiotic modifications made within the first hour after randomization, as these changes may be in response to Gram stain result rather than AXDX result
- 30-day readmission to the index hospital
- The proportion of discrepancies (as detailed in 6.0) between rapid testing and standard of care testing among subjects who receive rapid testing (arm 2)
- Antibiotic intensity score (as detailed in 5.5.3) in the first 72 hours post randomization

- Desirability of outcome response and response adjusted for antibiotic risk within 72 hours (DOOR-RADAR) score (see Table 7 below)

Table 7. Desirability of outcome response (DOOR) ranking table.

DOOR Rank	30-day mortality	In ICU at 72h post-randomization	HO-CDI*	New resistant or hospital-acquired organism**
1	Alive	No	No	No
2	Alive	No	Yes	No
3	Alive	No	No	Yes
4	Alive	No	Yes	Yes
5	Alive	Yes	No	No
6	Alive	Yes	Yes	No
7	Alive	Yes	No	Yes
8	Alive	Yes	Yes	Yes
9	Dead	--	--	--

*HO-CDI, Hospital onset *C. difficile* infection

**Newly acquired within 30 days post-randomization, from clinically collected or surveillance cultures

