7.3 Sample Size

The study is designed to detect a difference in primary outcome, mean time to first antibiotic modification in the first 72 hours after randomization. We plan to enroll 500 unique participants (250 in each arm) in order to have at least 200 evaluable participants in each arm. Participants who died prior to randomization, were on comfort care at time of randomization, had GNB bacteremia at same or different institution within 7 days prior to randomization, or who were erroneously randomized due to laboratory issues such as spurious Gram stain result, will be considered unevaluable. This will provide 80% power with a 2-sided alpha=0.05 test, to detect a difference in the time to first modification of antibiotic therapy between the two arms of at least 9 hours, with a standard deviation (SD) of 32 hours. With 500 participants, if the SD is larger than 32 hours, there will still be sufficient power to detect a difference between the arms of 10 or more hours (see Table 8).

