7.4 Analysis

7.4.1 Analysis of primary outcome

We will calculate the mean difference in time to first antibiotic modification within 72 hours post randomization in both treatment arms, together with a 95% confidence interval. Patients who do not have antibiotic modifications will be assigned a time of 72 hours. The primary test will be a t-test (relying on a normal approximation, allowing for unequal variances in the treatment groups) for whether the mean of the primary outcome is different between the arms. We will also carry out a Wilcoxon rank-sum test, to compare the distribution of the time to first antibiotic modification between the arms without the assumption of normality. We will estimate the probability of having an escalation or de-escalation of antibiotics between 0 and 72 hours after randomization using the empirical cumulative distribution function with pointwise 95% confidence intervals.

The primary analysis will be a modified intention to treat analysis (ITT). Participants who died prior to randomization, were on comfort care at randomization as assessed by the study coordinator, had GNB bacteremia at same or different institution within 7 days prior to randomization, or whose blood culture had erroneous Gram stain results in the laboratory will be considered unevaluable. These are all issues which may not be known to the laboratory technologist at the time of randomization and would otherwise be exclusion criteria. Participants randomized to the rapid testing arm will be analyzed as randomized, including cases where the rapid test does not return a result.

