7.4.2 Analysis of secondary and exploratory outcomes

We will compare all secondary and exploratory outcomes between the rapid testing and standard testing arms. Where interest lies in mean differences, we will follow the same approach as for the primary outcome. The DOORs will be compared between arms to estimate the probability (with 95% CI) that a randomly selected participant will have a better DOOR outcome if assigned to rapid testing. We will determine the proportion of very major errors and very major or major errors among patients who receive rapid testing.

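### Giving early deaths the highest survivor intensity score suits a rank test but not a mean; Section 7.4.2 should name the rank comparison as the lead analysis

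*Combined protocol and SAP*

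**What the plan says.** Section 5.5.3 ranks each antibiotic from 1 to 5 and multiplies the rank by hours received in the 72 hours after randomization. For a patient on several drugs the total "score will be the summation of the rank x duration product for each antibiotic". The number of drugs is not capped. For early deaths the rule is: "Patients who die before 72 hours will be assigned the highest intensity score among patients in the study who were alive at 72 hours".

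Section 7.2.3 lists the score as exploratory: "Antibiotic intensity score (as detailed in 5.5.3) in the first 72 hours post randomization".

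Section 7.4.2 gives one general rule that could apply to it: "Where interest lies in mean differences, we will follow the same approach as for the primary outcome". In Section 7.4.1 that approach is a mean difference with a 95% confidence interval. "The primary test will be a t-test (relying on a normal approximation, allowing for unequal variances in the treatment groups") is followed by a second test: "We will also carry out a Wilcoxon rank-sum test, to compare the distribution of the time to first antibiotic modification between the arms". No sensitivity analysis of the death rule is described.

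**The concern.** Assigning deaths the worst value is sound when only order matters. In a mean, the size of the assigned value matters too, and here it is a sample maximum. A patient who dies a few hours after randomization on one narrow drug would be entered as the joint heaviest antibiotic user in the trial, and one survivor on several broad drugs would fix that entry for every early death. The primary outcome differs: patients without a modification get 72 hours, a limit set in advance.

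Antibiotic utilization is a secondary objective (Section 3.2). The synopsis lists duration of broad-spectrum gram-negative coverage, but Section 7.2.2 defines no such outcome. The intensity score is therefore the only defined measure of total antibiotic exposure, and readers may rely on it more than its exploratory label suggests.

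**Working it through.** **The plan's own figure.** Section 7.3 gives a power statement for the primary outcome only: "This will provide 80% power with a 2-sided alpha=0.05 test", for a difference of "at least 9 hours, with a standard deviation (SD) of 32 hours". With 200 evaluable per arm, SE = 32 × √(2/200) = 3.2 and 9/3.2 = 2.81. Power = Φ(2.81 − 1.96) ≈ 80%, so the figure reproduces. There is no corresponding figure for the intensity score. Its mean, SD, maximum and 72-hour death rate below are all assumptions.

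**Shift per excess early death.** Shift in an arm mean = (assigned maximum − arm mean) / 200.

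- Model A uses the Section 7.3 mix and times. Assumed ranks go from 4 to 2 on de-escalation, 2 to 5 on escalation, and stay at 3 with no change; 40% also receive a rank-1 drug and 10% a rank-3 drug for part of the window. Simulated means are about 236 (rapid) and 256 (standard), a difference of −20 around a midpoint of 246, with a maximum near 562.
- With that maximum: (562 − 246)/200 = 1.58 points.
- If one survivor has 13 rank points for the full window, the maximum is 13 × 72 = 936 and the shift is (936 − 246)/200 = 3.45 points.
- Six excess deaths in the rapid arm: 6 × 1.58 = 9.5, or 6 × 3.45 = 20.7, against a true −20.
- Model B assumes gamma scores with mean 250 and SD 100. Maxima of 432 to 1008 (72 h × summed rank 6 to 14) give (432 − 250)/200 = 0.91 to (1008 − 250)/200 = 3.79 points. The SE of the difference before deaths is 100 × √(2/200) = 10, so 1.96 SE equals 19.6/0.91 ≈ 21.5 down to 19.6/3.79 ≈ 5.2 excess deaths.

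**How often six or more excess deaths arise by chance.** With equal true death rates and 200 per arm, the exact binomial probability is about 2.5%, 8% and 12% in one given direction at rates of 2%, 4% and 6%. In either direction it is about 5%, 16% and 25%.

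**Power with equal death rates** (simulation, 200 per arm):

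| Model | Early deaths per arm | t-test | Wilcoxon |
|---|---|---|---|
| A, true −20 | 0 / 2 / 4 / 6% | 62 / 51 / 44 / 39% | 93 / 92 / 89 / 86% |
| B, true −30, maximum as simulated | 0 / 1 / 3 / 5% | 89 / 85 / 72 / 64% | 88 / 86 / 81 / 79% |
| B, true −30, one survivor at 1008 | 1 / 3 / 5% | 70 / 44 / 34% | 85 / 82 / 79% |

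Two rebuilds of Model A gave t-test power of 59 to 62% without deaths and 36 to 37% at 6% deaths. With no true effect and equal death rates of 1 to 5%, the t-test in Model B rejected in 4 to 6% of runs.

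**Unequal death rates** (Model B, 3% standard, 6% rapid). The expected artefact with a maximum of 1008 is about 0.03 × (1008 − 250) = 22.7 points. With no effect among survivors, the simulated mean difference was 12 points with the natural maximum and 23 with 1008. The t-test rejected in 14% and 23% of runs, Wilcoxon in about 9%. With a true 30-point reduction, the estimated reduction shrank to 17 and 5 points.

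**The case against.** Much of the opposing case stands.

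- A reader might infer that the plan fixes the t-test for this score. It does not: the sentence in 7.4.2 is conditional and the score is not named. The mean-first reading is the natural one only because no other rule fits a continuous total.
- The approach already includes a Wilcoxon test, and giving deaths the survivor maximum puts them tied at the top. The rank comparison recommended here is nearly the one already available; what changes is its place.
- A reader might also infer that the result is driven by death counts and one extreme patient. The documents cannot show that, because they give neither a 72-hour death rate nor a score distribution. With equal death rates the type I error holds and the loss is power, on an outcome for which the plan claims none. Six excess deaths is 3 percentage points of 200, and cancelling the whole −20 also requires the hypothetical maximum of 936.
- In Model A the t-test trails Wilcoxon by 31 points with no deaths at all. That gap comes from the assumed score mixture. Only the further fall is due to the death rule.
- Excluding comfort-care patients (7.4.1) would remove some early deaths if the same population is used for this score.
- Counting death as worst is a defensible composite: it stops early death from looking like low antibiotic use.

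The last argument supports the rule for ranks. It does not justify entering an arbitrary, data-dependent number into a mean. Nor does the presence of Wilcoxon as a second test correct the mean difference and interval that would be reported first.

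**Conclusion.** The point holds as a matter of method, conditional on the score being analysed by the primary-outcome approach. The mean difference would then combine antibiotic use with early mortality and be sensitive to one extreme survivor. With equal death rates the harm is lost t-test power: about 62% to 39% at 6% early deaths in Model A and 89% to 64% at 5% in Model B, while Wilcoxon loses much less. A shift in the estimate requires an imbalance in early deaths, about 1.6 to 3.45 points per excess death under Model A's assumed maxima. All these sizes rest on assumed distributions. The rank comparison is still a composite of use and death, but it does not depend on how extreme the top survivor is. The outcome is exploratory, and no primary or secondary conclusion depends on it. The change is worth making because it is specific and costs little.

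**What to change.** Add to Section 7.4.2:

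- The lead analysis of the stand-alone intensity score is the Wilcoxon rank-sum comparison, with deaths before 72 hours ranked worst.
- The imputed sample maximum is not used in any mean or t-test.
- The mean difference among patients alive at 72 hours is reported as a descriptive sensitivity analysis, with early deaths shown by arm.

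DOOR is unaffected, since Table 7 already ranks death last.

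Rescaling to score per hour alive × 72 is not a good substitute. It extrapolates, and it clashes with the one-hour convention for single doses in 5.5.3. Death at 30 minutes after single doses of a rank-4 and a rank-1 drug would score (4 + 1)/0.5 × 72 = 720, above Model A's maximum of 562.

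The cost is a few SAP sentences and no new data. The headline for this exploratory measure becomes a rank comparison, and the survivors-only mean is conditional on survival, so it should not be read as a randomized comparison of all patients.

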5.5.4 Outcomes

Final outcomes for each enrolled patient will be gathered retrospectively from the EMR. Patients will be followed for the duration of their hospitalization, or up to 30 days if they remain hospitalized.

Inpatient hospitalization cost data will be obtained from Vizient/University Health Consortium (UHC).

6.0 Monitoring

The site Microbiology Laboratory Director is responsible for monitoring and reviewing discordant results between the rapid and standard test methods for subjects in arm 2. AST discrepancies will be categorized as follows:

- **Very major errors:** susceptible by rapid test method and resistant by standard culture/AST.
- **Major errors:** resistant by rapid test method and susceptible by standard culture/AST
- **Minor errors:** intermediate by one method and susceptible or resistant by the other method

Sites will record all errors.

Discrepancies between the rapid and standard results will be handled as noted in section 5.3.3.

The proportion of discrepancies between testing methods for individual bacteria-drug combinations classified as very major errors, major errors, or minor errors will be calculated. Acceptable performance will be categorical agreement $\geq 90\%$, very major errors $\leq 3\%$ and major errors $\leq 3\%$.²¹.

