1.0 Background Information and Scientific Rationale

1.1 Background Information

Novel molecular diagnostics to identify bacteria and determine antimicrobial susceptibility from clinical cultures are quickly entering the arsenal of tools used by clinical microbiology laboratories. However, the clinical benefit of these methods has not been well-quantified.

The goal of this study is to determine the impact of rapid bacterial identification and phenotypic antimicrobial susceptibility testing (AST) on antimicrobial usage and clinical outcomes.

The Accelerate PhenoTest™ BC Kit, performed on the Accelerate Pheno™ System (together termed AXDX) (Accelerate Diagnostics, Tucson, AZ) is an FDA-approved fully automated platform that performs rapid bacterial identification within 1.5 hours followed by determination of minimum inhibitory concentration (MIC)-based phenotypic susceptibility within approximately 7 hours directly from positive blood cultures.¹ This novel system uses fluorescence *in situ* hybridization (FISH) for rapid bacterial identification for a panel of organisms followed by time-lapse microscopy for determining phenotypic AST directly from positive blood culture bottles (see Table 1). In a study of 1850 blood cultures with gram-positive, gram-negative, or yeast isolates, AXDX was found to have overall 97.4% sensitivity and 99.3% specificity for organism identification compared to conventional culture methods (see Table 2). Among 728 gram-negative isolates, AXDX had 97.6% sensitivity and 99.6% specificity for pathogen identification, and had excellent essential (device result agrees exactly with or within one two-fold dilution of the reference result) and categorical (the device and reference result interpretive categories agree) agreement with the gold-standard methods for drug susceptibility testing, according to Food and Drug Administration (FDA) and/or Clinical and Laboratory Standards Institute (CLSI) breakpoints (see Table 3)¹.

Table 1. FDA-approved gram-negative bacilli and antibiotic combinations available on AXDX

	Ampicillin-sulbactam	Piperacillin-tazobactam	Cefepime	Ceftazidime	Ceftriaxone	Ertapenem	Meropenem	Amikacin	Gentamicin	Tobramycin	Ciprofloxacin	Aztreonam
E coli	x	x	x	x	x	x	x	x	x	x	x	x
Klebsiella spp.*	x	x	x	x	x	x	x	x	x	x	x	x
Enterobacter spp.*		x	x	x	x	x	x	x	x	x	x	x
Proteus spp.*	x	x	x	x	x	x	x	x	x	x	x	x
Citrobacter spp.*		x	x	x	x	x	x	x	x	x	x	x
S. marescens		x	x	x	x	x	x	x	x	x	x	x

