P. aeruginosa		x	x	x			x	x	x	x	x	
A. baumannii		x						x				

**Klebsiella spp.* includes *pneumoniae* and *oxytoca*; *Enterobacter spp.* includes *cloacae* and *aerogenes*; *Proteus spp.* includes *mirabilis* and *vulgaris*; *Citrobacter spp.* includes *freundii* and *koseri*

Table 2. Clinical trial results of AXDX performance for gram-negative bacilli identification (N = 728)

Organism	Sensitivity (%)	Specificity (%)
A. baumannii	98.6	99.7
Citrobacter spp.	96.8	99.3
E. coli	97.3	99.7
Enterobacter spp.	97.3	99.5
Klebsiella spp.	96.1	99.6
P. aeruginosa	100	99.4
Proteus spp.	97.7	99.6
Serratia marcescens	100	99.9
Gram-negative bacilli, total	97.6	99.6

Table 3. Clinical trial results of AXDX performance for gram-negative bacilli antibiotic susceptibility.

Antibiotic	EA (%)	CA (%)	# of fresh isolates	# of challenge isolates
Amikacin	93.8	93.8	202	200
Ampicillin-sulbactam	91.0	82.7	174	92
Aztreonam	96.4	97.6	198	137
Cefepime	96.2	95.5	215	209
Ceftazidime	92.4	92.1	203	163
Ceftriaxone	94.7	96.4	180	124
Ciprofloxacin	98.4	98.4	216	209
Ertapenem	98.8	98.5	200	139
Gentamicin	99.5	98.7	207	165
Meropenem	96.7	96.9	215	208
Piperacillin-tazobactam	91.0	90.8	207	205
Tobramycin	96.3	96.0	210	165

EA, essential agreement; CA, categorical agreement; challenge isolates with key resistance phenotypes and genotypes were seeded into blood culture broths.

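### Do the 3% error limits in section 6.0 need stated denominators and a minimum count before they can be used?

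*Combined protocol and SAP*

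**What the plan says.** Section 6.0 asks the site laboratory director to review discordant susceptibility results in arm 2. It defines a very major error as "susceptible by rapid test method and resistant by standard culture/AST" and a major error as "resistant by rapid test method and susceptible by standard culture/AST"; a minor error has an intermediate reading by one method only. It continues: "The proportion of discrepancies between testing methods for individual bacteria-drug combinations classified as very major errors, major errors, or minor errors will be calculated". The next sentence, opening "Acceptable performance will be categorical agreement", sets at least 90% for agreement and at most 3% each for very major and major errors, and cites reference 21, a guideline on verifying commercial identification and susceptibility testing systems.

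Two later sections return to the measure. Section 7.2.3 lists it among the exploratory analyses: "The proportion of discrepancies (as detailed in 6.0) between rapid testing and standard of care testing", in arm 2. Section 7.4.2 promises "the proportion of very major errors and very major or major errors among patients who receive rapid testing". Neither names a denominator. The combined very major or major category has no limit in 6.0.

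**The concern.** A percentage limit means little without its base, and here several bases are possible. Read literally, 6.0 could make the discrepancies themselves the denominator. Section 7.4.2 could be read as a proportion of patients. The two natural choices for very major errors are all paired results and standard-resistant results; by 6.0's own definition such an error can occur only among the latter. Section 7.4.2 does not decide between them. Its combined category cannot be a share of standard-resistant results, because a major error is susceptible by the standard method, but the two proportions need not share a base.

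Over all pairs, the limit partly measures how rare resistance is, so a test that misses many resistant isolates can pass. Over standard-resistant results, counts in one arm are so small that a single error usually fails the limit and zero errors passes with a very wide interval. If the base were chosen after the data were seen, the statement on acceptable performance could go either way.

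**Working it through.** The 3% limit is set, not derived, so there is no calculation in the plan to reproduce. The check is how much the choice of base matters at arm 2's size.

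**Inputs from the plan.** Arm 2 has 250 enrolled and at least 200 evaluable (7.3). Table 1 has 8 organism groups and 12 + 12 + 11 + 12 + 11 + 11 + 8 + 2 = 79 organism-drug cells. This is an upper bound, because 5.3.3 suppresses combinations that a laboratory does not routinely report. Categorical agreement by drug is in Table 3.

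**Assumptions.** The plan gives no organism mix, resistance rate or true miss rate for arm 2. I take one isolate per patient, a common species with 125 isolates, resistance of 5%, 10% or 20%, and a true miss rate of 10% among resistant results.

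**1. Where one error fits within 3%.** 1/33 = 3.03% and 1/34 = 2.94%, so one error is allowed only if the denominator is at least 34. Below 34 pairs, both bases allow zero errors and the verdict is the same.

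**2. How many groups reach 34 pairs.** Spread evenly, 250/8 = 31.25 or 200/8 = 25 isolates per group. Eight groups of 34 would need 272. At most 7 groups can reach 34 with 250 isolates, and at most 5 with 200.

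**3. How often 34 resistant results occur.** If every patient had the same species, resistance of 34/250 = 13.6% or 34/200 = 17% would be needed; for 125 isolates, 34/125 = 27.2%. Over standard-resistant results the limit is therefore close to a zero-error rule almost everywhere.

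**4. Leniency over all pairs.** The share of resistant results that can be missed is 0.03/p, where p is the resistance rate: 60%, 30% and 15% at p = 5%, 10% and 20%. This needs enough pairs for the 3% to allow an error.

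**5. Chance of passing, 125 isolates.** Over all pairs 3 errors are allowed (3/125 = 2.4%; 4/125 = 3.2%). Over the resistant results below, none is. With X ~ Bin(n, 0.10):

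| Resistance | Resistant results, n | All pairs: P(X ≤ 3) | Resistant only: P(X = 0) |
|---|---|---|---|
| 5% | 6 | 99.9% | 53% |
| 10% | 12 | 97% | 28% |
| 20% | 25 | 76% | 7% |

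So for a common species with low to moderate resistance, the base can change the likely verdict.

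**6. The plan's own agreement figures.** Over all pairs, very major errors cannot exceed 100% minus categorical agreement. Table 3 leaves 1.3% for gentamicin, 1.5% for ertapenem, 1.6% for ciprofloxacin and 2.4% for aztreonam; the next is meropenem at 3.1%. For 4 of 12 drugs the limit could not be failed at that agreement. These figures are by drug and mix fresh isolates with challenge isolates chosen for resistance, so they only illustrate single combinations in arm 2.

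**7. Whether a minimum of 34 would help.** It marks where 1/n falls below 3%; it is not a precision criterion.

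- A result of 1/34 passes with an exact 95% upper limit of 15.3%, and 0/34 passes with 10.3%.
- With 12 resistant results, a test with a true 1% error rate fails with probability 1 − 0.99^12 = 11%.
- With 66 resistant results, where one error is allowed, the same test fails with probability 1 − P(X ≤ 1) = 14%.

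By steps 2 and 3, such a rule would also leave most combinations with no very major error verdict.

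**The case for a change.** The strongest case for a change is that the plan commits to more than a description. It sets a standard of acceptability, and step 5 shows that one and the same test could probably pass on one base and fail on the other. The reader cannot tell from the plan which was meant, and the guideline's content cannot be checked from these documents. Naming the base would cost a sentence. Arm 2 has both tests on the same blood culture and sites record all errors, so no new data would be needed.

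The omission and the arithmetic both stand, and stating the base would be tidier. They do not show that the plan would lead anyone astray. Attaching a verification guideline to acceptance limits is a normal way to bring in its definitions. If the guideline left the point open, an analyst could still give the numerator, the base and an exact interval, and the reader could see what the percentage means. The contrast also depends on an assumed common species with low to moderate resistance; for smaller combinations the two bases agree.

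**Conclusion.** The gap is real but small, and analysts can fill it sensibly; no change to the plan is needed. The base could alter the very major error verdict for a few common combinations, by as much as 97% against 28% in the chance of passing under the assumptions above. Below 34 pairs it alters nothing, and any verdict there is very imprecise (0/12 has an exact 95% upper limit of 26.5%).

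Nothing in the trial turns on that verdict. The measure is for monitoring and exploration, and no study-level consequence of missing a limit is stated. Section 5.3.3 deals with each discordant result individually, whatever the overall proportion. Sections 5.1 and 8.1 say that the assay's accuracy or performance is not the question. The time to antibiotic modification and all secondary outcomes are computed without it.

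The one proposal that goes beyond writing down a definition, a minimum count of 34 with no verdict below it, is at best a trade-off: it removes most verdicts and leaves the rest imprecise. This conclusion rests on the cited guideline, or failing that the analyst, supplying a conventional base, and on the error proportions being reported with their counts.
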